4.1.1 Baseline values

Baseline is the last measurement collected (including measurements taken at unscheduled visits) prior to the date and time of first dose of study medication at randomization visit (visit 4, week 0), or last measurement collected prior to randomization visit, for subjects who are randomized but do not receive any study medication. For in-clinic assessments with assessment date equal to the first dose of study medication and time not available, the assessment will be assigned to the baseline period since all assessments are to be done prior to dispensing study medication according to the protocol. For AEs and concomitant medications with start date equal to the first dose of study medication and time not available, the event will be considered post-baseline.

4.1.2 Change and percent change from baseline

Change in any measurement (CM) from baseline to any randomized treatment period *Week t* is defined as follows:

$$CM_{Week\ t} = M_{Week\ t} - M_{baseline},$$

where:

- $CM_{Week\ t}$ is the change in the measurement from baseline at *Week t*,
- $M_{Week\ t}$ is the measurement at *Week t*,
- $M_{baseline}$ is the baseline measurement.

Percent change in any measurement (PCM) from baseline to any randomized treatment period *Week t* is defined as follows:

$$PCM_{Week\ t} = 100 \times (M_{Week\ t} - M_{baseline}) / M_{baseline}.$$

4.1.3 Creatinine clearance

Creatinine clearance (CrCl) from serum creatinine will be calculated using the following formulae

$$\text{Male: } \frac{(140 - \text{age}) * \text{weight in kg}}{72 * \text{creatinine in } \mu\text{mol/L}} * 0.01131$$

$$\text{Female: } \frac{(140 - \text{age}) * \text{weight in kg}}{85 * \text{creatinine in } \mu\text{mol/L}} * 0.01131$$

4.1.4 Last observation carried forward (LOCF)

In LOCF analyses at Week t, the measurement designated as the Week t measurement will be used. If no Week t measurement is available, the last available earlier post-baseline measurement will be used.

4.1.5 Analysis of covariance (ANCOVA) model for percentage change from baseline

For the secondary efficacy analyses of lipid and lipoprotein outcome measures in the study, the ANCOVA model of percentage change from baseline to Week 104 (or last visit during treatment) efficacy will include treatment as a main effect and baseline value as a covariate. The following model will be used:

$$C_{ij} = \text{intercept} + \beta M_{\text{baseline},ij} + \tau_j + \varepsilon_{ij},$$

Where -

- C_{ij} is the percent change from baseline to Week 104 of subject i in treatment group j
- β is the slope of C_{ij} regressing on the baseline measurement
- $M_{\text{baseline},ij}$ is the baseline measurement of subject i , in treatment group j
- τ_j is the main effect of treatment group j
- ε_{ij} is random error

The ANCOVA will present least squares (LS) mean estimates and 2-sided 95% confidence intervals (CIs) for mean percent changes from baseline within and (when warranted) between the rosuvastatin and placebo treatments groups. In addition, t-statistics corresponding to the Type III sums of squares for the difference in the LS means will be used to obtain p-values for treatment group comparisons for certain efficacy analyses.

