#### **8.5.1 Analysis of the primary efficacy variable**

A linear mixed-effects model will be used for the primary analysis to assess the difference in the annualized rate of change in the CIMT measurements across 12 carotid artery sites between rosuvastatin 20 mg and placebo treatment over 104 weeks.

For the primary efficacy analysis, the dependent variable is the maximum CIMT measurement from 3 interrogation angles at each of the 12 carotid artery sites at each timepoint of CIMT measurement during the 104-week study period. The model includes fixed effects for treatment group, time, time by treatment interaction, ICVD risk stratification (<5%/5% to 10%), age, sex, centre and scan reader, and random effects for the intercept and slope at the individual subject level and carotid artery site within subject. Ultrasound machine will be included as a fixed effect as well if different types of machines are deployed across sites. For time of CIMT measurement, the 2 pre-randomization visits and the final 2 visits at the end-of-study will be treated as separate time points. Details will be defined in the Statistical Analysis Plan. Time, as a continuous variable, is the interval from the date of randomization to the date of CIMT measurement. Differences in annualized change between rosuvastatin and placebo will be evaluated by testing the time-by-treatment interaction term.

In the analysis, let  $\beta_1$  and  $\beta_2$  represent respectively the coefficient parameters for time and time by treatment interaction in the mixed effect model. The annualized rate of change (slope) in MeanMax CIMT in placebo will be estimated by the coefficient parameter  $\beta_1$ , the annualized rate of change (slope) in MeanMax CIMT in rosuvastatin will be estimated by  $\beta_1 + \beta_2$ , and the difference of annualized rate (slope) of change between 2 groups will be estimated by  $\beta_2$ . Then, the null and the alternative primary hypothesis can be expressed as  $H_0: \beta_2 = 0$  vs.  $H_a: \beta_2 \neq 0$  at a significance level of 0.05 two-sided.

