### 8.5.2 Analysis of the secondary efficacy variables

The same statistical method used for the primary CIMT efficacy analysis will be applied to model the segment-specific secondary CIMT efficacy outcome measurements. The difference in the annualized rate of change between rosuvastatin and placebo for the secondary CIMT outcome measures will also be evaluated by testing the time-by-treatment interaction term in each model fitting.

Secondary lipid and lipoproteins outcome measures are the percentage change from baseline, which will be analyzed by analysis of covariance with terms for treatment in the model. For lipid measurements (LDL-C, total cholesterol, HDL-C, triglycerides, non-HDL-C, non-HDL-C/HDL-C), both the analysis of the percent change from baseline at final visit, and the analysis of the percent change from baseline to time-weighted average during treatment will be performed. In the evaluation of change from baseline to final visit, missing observations will be imputed by last observation carried forward (LOCF). The time-weighted average lipid value is defined as the lipid value multiplied by the number of days since the last lipid assessment, summed for all lipid observations and divided by the sum of days between all visits. No imputation will be made for lipid missing values for time-weighted average analysis. For apolipoprotein measurements (ApoB, ApoA-I, ApoB/ApoA-I), the analysis of the percent change from baseline to final visit (LOCF) will be performed.

No multiplicity adjustment will be applied to the secondary efficacy analysis.

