4.3 Efficacy analysis

CIMT Data

In this study the CIMT data has a hierarchical (or multilevel) structure. The levels for the data are defined by 1) the study participants and 2) carotid artery sites within the participants. The repeated measure is time.

A multi-level, linear mixed-effects model will be used for the primary analysis to assess the difference in the annualized rate of change in the CIMT measurements across 12 carotid artery sites between rosuvastatin 20 mg and placebo treatment over 104 weeks. The model is specified in terms of fixed effects for randomized treatment group, time, time by treatment interaction, ICVD risk stratification (<5%/5%-10%) – based on IxRS data, carotid artery site,

age, sex, centre, and scan reader (In the unlikely event that the model does not converge it may be necessary to drop fixed effects for reader, sex and age in that order). Random effects within the model are the intercept and slope for individual subjects. Time in the model is a continuous measure and is the interval in years from date of randomization to date of CIMT measurement and its effect is linear.

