4.3.5 Laboratory data

Analyses of percentage change from baseline in lipids and lipoproteins will be carried out for the ITT population using ANCOVA with terms for treatment and baseline value as a covariate in the model. For LDL-C, this will be analysed for both sets of LDL-C values (collected and converted) described in section 4.1. However, the converted values will be considered as the secondary endpoint while the collected values will be used for supportive analysis.

The assumptions of normality and homogeneity of variance will be explored using probability and residual plots. If assumptions are found to be violated, rank ANCOVA approach (Quade 1967) will be used.

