4.3.7 Subgroup analyses

The effects of rosuvastatin in following subgroups of subjects will be evaluated,

1. Age: < 65 and ≥ 65 years
2. Sex
3. BMI: < 28 vs ≥ 28 kg/m²
4. China Adult Dyslipidemia Management Guidelines ICVD risk categories (see 4.2.2 for definitions)
5. History of hypertension (Yes/No)
6. Baseline LDL-C: below and above or equal to the mean
7. Baseline TC: below and above or equal to the mean
8. Baseline HDL-C: below and above or equal to the mean
9. Baseline TG: above and below the mean (If TG are not normally distributed, groupings above and below the median value will be considered).
10. Baseline non-HDL-C: below and above or equal to the mean
11. Baseline non-HDL-C/HDL-C: below and above or equal to the mean
12. Baseline ApoB: below and above or equal to the mean
13. Baseline ApoA-I: below and above or equal to the mean
14. Baseline ApoB/ApoA-I: below and above or equal to the mean
15. Smoking: never, current/former

The treatment-by-subgroup interaction will be examined by adding the subgroup variable and the interaction term of treatment-by-subgroup as covariates to multilevel, repeated measures, linear mixed effects model as described for the primary analysis (section 4.3). Similar output will be presented for each subgroup as for the primary analysis. When the subgroups are also stratification factors, the eCRF values will be used rather than the values from IxRS used for randomization.

For smoking subgroup, if there is any category with less than 10% of the population in a review prior to unblinding the study, the subgroup may be re-categorized or eliminated before unblinding.

These analyses will use the ITT analysis set.

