Appendix C SAS codes for statistical models used in the efficacy analysis.

Multi-level linear mixed effects model for primary efficacy analysis:

```
PROC MIXED;
CLASS TRT SITE SUBJID ICVD SEX READER CENTRE;
MODEL RESPONSE = TRT TIME TRT*TIME ICVD SITE CENTRE AGE SEX READER
/ SOLUTION DDFM = KR CL COVB;
RANDOM INTERCEPT TIME /SUB = SUBJID TYPE = UN;
RUN;
```

Note: The maxCIMT value for each site will be the dependent variable (RESPONSE) in the mixed effects model. Time is a continuous variable per the protocol and will be the interval in years from date of randomization to date of the CIMT measurement. The fixed effect Time in the MODEL statement is not declared as a class variable; thus it models a linear trend in time. We want to see the change in slope over time for the difference between rosuvastatin and placebo across all sites.

The TYPE=UN option in the RANDOM statement specifies an unstructured covariance matrix for the random intercept and slope effects at the individual subject level.

[figure not shown]
ANCOVA analyses for the laboratory efficacy endpoints:

[figure not shown]
```
PROC GLM;  
CLASS TRT;  
MODEL PER_CHG = TRT BASE /CLPARM;  
LSMEANS TRT / STDERR PDIFF CL;  
ESTIMATE 'ROSUVASTATIN 20 MG VS PLACEBO' TRT 1 -1/CL;  
RUN;
```

PER_CHG = Percentage change from baseline
TRT = Randomized treatment
BASE = Baseline value

[figure not shown]

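### The lipid and apolipoprotein ANCOVA leaves out the ICVD-risk stratum that the CIMT model includes; adding it may narrow the intervals slightly and costs one degree of freedom

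*SAP*

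**What the plan says.** **Lipid and apolipoprotein model.** SAP 4.1.5 states that the model "will include treatment as a main effect and baseline value as a covariate", and its equation has an intercept, a baseline slope, a treatment effect and an error term. SAP 4.3.5 describes it as "ANCOVA with terms for treatment and baseline value as a covariate in the model". The Appendix C code is "MODEL PER_CHG = TRT BASE /CLPARM", with treatment as the only class variable. SAP 4.1 and Appendix B agree. Protocol 8.5.2 asks only for "analysis of covariance with terms for treatment in the model", so the baseline value was added in the SAP. The model serves nine endpoints: LDL-C, total cholesterol, HDL-C, triglycerides, non-HDL-C, ApoB, ApoA-I and the two ratios.

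**CIMT model.** Protocol 8.5.1 lists "ICVD risk stratification (<5%/5% to 10%), age, sex, centre and scan reader" among the fixed effects. SAP 4.3 repeats the ICVD factor and says it comes from IxRS data. The Appendix C code is "MODEL RESPONSE = TRT TIME TRT*TIME ICVD SITE CENTRE AGE SEX READER".

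**Randomisation.** Protocol 3.3 gives a 1:1 ratio. Protocol 3.5, on the method of assignment, is redacted. SAP 4.2.3 summarises the ICVD category from both IxRS and eCRF data. SAP 4.3.7 lists that category as a subgroup and says: "When the subgroups are also stratification factors, the eCRF values will be used rather than the values from IxRS used for randomization".

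**The concern.** When allocation is stratified by a factor, the arms are balanced on it by design. An analysis that includes the factor takes account of that balance. An analysis that omits it leaves any outcome variation due to the factor in the residual, so the reported standard error exceeds the true sampling variability of the treatment difference. Intervals are then a little too wide, and the test rejects a true null slightly less often than 5%.

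The same SAP adjusts for the ICVD stratum in the CIMT analyses and not in the lipid analyses, and the readable text gives no reason. What is at stake is a small amount of precision on secondary endpoints, and a possible later question about why adjustment differs between the two families of endpoints.

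**Working it through.** The plan states no figure that depends on this point. The sample-size sections are redacted, and no standard deviation or effect size is given for any lipid endpoint. The size must therefore rest on assumptions.

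**From the documents:** N = 543 randomised (protocol synopsis), 1:1 allocation, two ICVD strata, significance level 0.05 (two-sided for the primary hypothesis in protocol 8.5.1, and carried over here).

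**Assumed:** residual SD of percent change, given treatment, baseline and stratum, s = 15 to 25 points; share of one stratum p = 0.3 to 0.5; difference between strata after baseline adjustment d = 0 to 10 points.

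**Formulas under stratified allocation:**
- Standard error with the stratum in the model: 2s/√N. For s = 20: 40/√543 = 1.717.
- Ratio of the model standard error without the stratum to that with it: r = √(1 + p(1−p)d²/s²).
- Share of residual variance explained by the stratum: R² = 1 − 1/r².
- Narrowing of the interval when the term is added: 1 − 1/r = 1 − √(1−R²).
- Actual two-sided type I error without the term: 2[1 − Φ(1.96r)].

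| s | p | d | r | R² | Narrowing | Type I error without the term |
|---|---|---|---|---|---|---|
| any | any | 0 | 1.000 | 0 | 0 | 0.050 |
| 25 | 0.3 | 5 | 1.0042 | 0.8% | 0.4% | 0.049 |
| 20 | 0.5 | 5 | 1.0078 | 1.5% | 0.8% | 0.048 |
| 15 | 0.5 | 5 | 1.0138 | 2.7% | 1.4% | 0.047 |
| 20 | 0.3 | 10 | 1.0259 | 5.0% | 2.5% | 0.044 |
| 15 | 0.5 | 10 | 1.0541 | 10.0% | 5.1% | 0.039 |

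If the stratum explains at most 5% of residual variance, the interval narrows by at most 1 − √0.95 = 1 − 0.975 = 2.5%. The last row lies outside that range and needs a 10-point stratum difference with an SD of 15.

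**Power**, at s = 20 and p = 0.5, for a 5-point treatment difference: 0.830 with the term, against 0.826 (d = 5) or 0.814 (d = 10) without it. For a 10-point difference it is 0.9999 either way.

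**Simulation check:** 4,000 trials per setting, permuted blocks of four within stratum, s = 20, p = 0.5, baseline distribution differing by stratum.
- d = 10: mean model standard error 1.761 without the term and 1.717 with it; empirical SD of the estimate 1.723 and 1.719; mean estimate under the null −0.009 and −0.012; rejection rate 0.045 and 0.0495.
- d = 0: both models gave a standard error of 1.717, with rejection rates of 0.0455 and 0.0445.

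The Monte Carlo error of a rejection rate is about √(0.05 × 0.95/4000) = 0.0034, so the comparison of standard errors is the firmer evidence. The simulated ratio at d = 10 (1.761/1.717 = 1.026) is below the formula's 1.031 for p = 0.5, because the baseline covariate carries part of the stratum effect.

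**The case against.** The strongest case against raising this is that nothing in the plan is wrong. Every SAP statement of the lipid model agrees, the SAP already improves on the protocol by adding the baseline value, and the omission can only be conservative. The endpoints are secondary with no multiplicity claim, and the size rests wholly on assumptions whose range includes zero. All of this stands, and it limits the point to a minor improvement.

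A reader might also infer more than the documents support:

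- **That randomisation is stated to be stratified by ICVD risk.** Protocol 3.5 is redacted, and the sentence in SAP 4.3.7 is conditional and does not name the factor. Read with SAP 4.2.3 and 4.3 the inference is strong, but it remains an inference. Other factors, or a reason for the omission, may lie in redacted text. If allocation was not stratified, the standard error without the term would be valid, and the gain from adding it would be ordinary covariate precision.
- **That the strata must relate to these outcomes because they are built from lipid levels.** The risk count in protocol Appendix F uses HDL-C below 40 mg/dL, and the LDL-C entry ceilings differ (160 against 190 mg/dL). Those are screening levels, whereas the outcome is percent change given baseline, and for HDL-C and LDL-C the baseline covariate already holds much of that information. Some association remains plausible: obesity and smoking enter the count, and the on-study LDL-C limits for stopping treatment differ by risk group (protocol 3.9), which can affect which value is carried forward. None of this is shown.
- **That HDL-C, ApoA-I and triglycerides are hit hardest because their expected effects are small.** The documents give no expected effect sizes for them.

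**Conclusion.** The omission is real and consistent throughout the SAP. The lipid and apolipoprotein ANCOVA has treatment and baseline only, while the CIMT model also has the IxRS ICVD stratum.

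A reader might take this as a source of bias or of false positive findings. It is neither: under stratified allocation the treatment difference stays unbiased and the type I error stays at or below its nominal level. The only consequence is a standard error that may be slightly too large. With 0 to 5% of residual variance explained by the stratum (assumed), intervals would narrow by 0 to 2.5%; if the stratum predicts nothing after baseline adjustment, they would not narrow at all. No conclusion can be identified that would change. The point is worth acting on only because the remedy is almost free.

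**What to change.** Before unblinding, which is the limit that protocol 8.1 sets for final SAP amendments, add the IxRS ICVD stratum as a fixed factor to the lipid and apolipoprotein ANCOVA. In code this is `PER_CHG = TRT BASE ICVD`, with `ICVD` added to the `CLASS` statement. Make the change in all of these places, so that text and code still agree:

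- SAP 4.1, the general description;
- SAP 4.1.5, both the sentence and the model equation;
- SAP 4.3.5, including the rank-ANCOVA fallback, so that an endpoint failing the normality check is adjusted in the same way;
- Appendix B, the lipid and apolipoprotein rows;
- Appendix C, the SAS code.

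Use the IxRS value, as in the CIMT model, rather than the eCRF value reserved for subgroups. The existing treatment contrast needs no change. With a second class variable, the within-group least-squares means weight the two strata equally by default, so state the intended weighting; the treatment difference is the same either way.

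The cost is one degree of freedom: at most 543 − 3 = 540 residual degrees of freedom become 543 − 4 = 539. If the sponsor prefers the present model, one sentence giving the reason would do, with the adjusted model specified as a sensitivity analysis.

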#### **4.2.1 Visit 4 (Week 0; Baseline)**

Visit 4 at Week 0 is the Baseline visit. Subjects will be required to fast for 8 hours (water permitted) prior to Visit 4 (Week 0). Those subjects who have failed to fast for 8 hours should return for their blood draw following an 8-hour fasting period. At the visit, the following procedures will be performed:

- Randomization
- Recording of vital signs
- Measurement of body weight
- Recording of AEs
- Recording of concomitant medications
- Physical examination
- Electrocardiogram (ECG)
- Chemistry panel
- Hematology
- Urine sample for complete urinalysis
- Serum lipid profile

- ApoA-I and ApoB
- Dispense investigational product
- TLC counselling

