1.2 Study design

This study is a randomized, double-blind, placebo-controlled, multicenter parallel group study assessing the effects of rosuvastatin 20 mg treatment for 104 weeks on the change in CIMT of the common carotid artery (CCA), carotid bulb, and internal carotid artery (ICA) in adult Chinese subjects with subclinical atherosclerosis.

The timing of IMT measurements is detailed in section 3.1. Blood samples for analysis of lipid parameters will be collected at weeks -6, 0, 6, 13, 39, 65, 91 and at the time of discontinuation of study treatment (on or before week 104).

Figure 1 Study flow Chart

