4. ANALYSIS METHODS

4.1 General principles

All statistical evaluation, as well as summaries and tabulations will be done by qualified personnel at IQVIA. Before breaking the treatment codes, following clean file declaration, all decisions made on the evaluability of the data for each individual subject will be documented and each subject will be assigned to the appropriate analysis data set.

The primary analysis for efficacy variables will be based on the ITT analysis set. The CIMT analysis will be performed on the PP population as a robustness check of the analysis on ITT analysis set.

A multilevel, repeated measures, linear mixed effects model will be used for the analysis of the primary and secondary CIMT end points. Rationale for the choice of the model follows Espeland et al (1992 and 1999) and Pitt et al (2000). Details of the model are given in section 4.3.3.

No multiplicity adjustment will be applied to the secondary efficacy analysis.

Lipid and Apo analyses will be performed on the ITT analysis set only. The definition of baseline for laboratory endpoint variables is given in section 4.1.1.

Secondary lipid and lipoproteins outcome measures are the percentage change from baseline, which will be analyzed by analysis of covariance (ANCOVA) with terms for treatment as a factor and baseline value as a covariate in the model. For lipid measurements (LDL-C, total cholesterol, HDL-C, TG, non-HDL-C, non-HDL-C/HDL-C), both the analysis of the percent change from baseline at final visit, and the analysis of the percent change from baseline to time-weighted average during treatment will be performed. In the evaluation of change from baseline to final visit, missing observations will be imputed by last observation carried forward (LOCF) method. No imputation will be made for missing lipid values for time-weighted average analysis.

During the study, LDL-C measurement was transitioned from 2nd generation reagent to 3rd generation reagent by direct assay. Post-baseline LDL-C values will be affected. To evaluate the consistency of different measurement reagents, all post-baseline LDL-C related analysis will be performed on two sets of data.

- LDL-C values as collected, regardless of the type of reagent.

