Number	Important protocol deviations / Criteria	Complete/partial data exclusion
	Inclusion Criteria	
1.	
Enrolled, for male, subject < 45 years or ≥ 70 years
 
for female, subject < 55 years or ≥ 70 years
	Complete data exclusion.
2.	
Enrolled, even though subject did not meet the criteria below:
 
Subjects with only hypertension (as defined blood pressure ≥ 140/90 mmHg or on antihypertensive treatment) and age as cardiovascular disease (CVD) risk factors and also subjects without hypertension who have 3 or more other risk factors (including age) must have:
 
 – Fasting LDL C of ≥ 120 mg/dL (3.1 mmol/L) and < 160 mg/dL (4.1 mmol/L) (Note: if a subject meets this criteria during a re-test between visit 1 and 2, this is not considered a deviation) 
Subjects without hypertension who have fewer than 3 other risk factors (including age) must have:
 
 – Fasting LDL-C of ≥ 120 mg/dL (3.1 mmol/L) and < 190 mg/dL (4.9 mmol/L) (Note: if a subject meets this criteria during a re-test between visit 1 and 2, this is not considered a deviation) 
Subjects with hypertension and age as CVD risk factors, along with at least one other risk factor, will be considered as having an important protocol deviation, regardless of fasting LDL-C values at screening.
	Complete data exclusion.

Number	Important protocol deviations / Criteria	Complete/partial data exclusion
3	
Enrolled, even though subject did not meet the criteria below:
 
TG < 500 mg/dL (5.65 mmol/L) at visit 1 (week -6)
 
(Note: if a subject meets this criteria during a re-test between visit 1 and 2, this is not considered a deviation)
	Complete data exclusion.
4	
Enrolled, even though subject did not meet the criteria below:
 
HDL cholesterol levels ≤ 60 mg/dL (1.6 mmol/L) at visit 1 (week -6)
 
(Note: if a subject meets this criteria during a re-test between visit 1 and 2, this is not considered a deviation)
	Complete data exclusion.
5	
Enrolled, even though subject did not meet the criteria below:
 
Maximum IMT ≥ 1.2 mm and < 3.5 mm in the carotid ultrasound studies conducted at both visit 2 (week -4) and visit 3 (week -2).
	Complete data exclusion.
	Exclusion criteria	

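### The lipid ANCOVA is valid but leaves out the Visit 1 (Week -6) lipid value, which costs a modest, avoidable amount of precision on the six lipid secondary measures

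*SAP*

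**What the plan says.** **Model.** SAP 4.1.5 gives a model that "will include treatment as a main effect and baseline value as a covariate". SAP 4.1, 4.3.5 and Appendix B agree, and the Appendix C code is "MODEL PER_CHG = TRT BASE /CLPARM". Protocol 8.5.2 names treatment as the only term, so the SAP has already added one covariate.

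**Baseline.** SAP 4.1.1: "Baseline is the last measurement collected (including measurements taken at unscheduled visits) prior to the date and time of first dose". This is a single value, not an average.

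**Sampling.** SAP 1.2: "Blood samples for analysis of lipid parameters will be collected at weeks -6, 0, 6, 13, 39, 65, 91", and again when treatment stops. Protocol Table 1 and section 4.1.1 list the serum lipid profile at Visit 1, so each subject should have two pre-dose profiles, at Week -6 and Week 0. Protocol 3.1 sets the triglyceride and HDL-C entry limits at Visit 1. It names no visit for the LDL-C limit, but SAP Appendix A allows a re-test between Visits 1 and 2 to satisfy it, which places that check at screening.

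**Endpoints affected.** SAP 4.1: "For lipid measurements (LDL-C, total cholesterol, HDL-C, TG, non-HDL-C, non-HDL-C/HDL-C), both the analysis of the percent change from baseline at final visit" and the change to the time-weighted average (TWA) are analysed. These six measures have two pre-dose values. The apolipoproteins ("ApoA-I and ApoB" in Protocol 4.2.1) are first drawn at Visit 4 and have only one.

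**The concern.** One lipid result is a noisy reading of a subject's usual level. When it is the only covariate, its error flattens the fitted slope (regression dilution), and between-subject variation that a better estimate of the usual level would remove stays in the residual. The Visit 1 result is a second reading of that level. It is taken before randomisation and should be nearly complete, because entry depends on the lipid results at screening.

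The SAP follows this principle for CIMT: section 4.3.3 expects the two pre-randomisation scans to predict later values strongly and keeps both in the model. For lipids the second pre-dose value is dropped, and no reason is given.

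At stake is the width of the confidence intervals on six secondary measures. It matters least for LDL-C and more for HDL-C and triglycerides.

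**Working it through.** The documents give no SD, correlation, effect size or power for the lipid endpoints, so there is no figure of the plan's own to reproduce. Everything below except N = 543 randomised (Protocol synopsis) and the entry limits (Protocol 3.1) is an assumption.

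**1. Closed form (no entry limits, raw values, no treatment effect on variance).** Let ρ be the correlation between the Week -6 and Week 0 values, and r the correlation of either with the follow-up value. In units of the total variance:

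- residual variance with one pre-dose covariate: 1 − r²
- with two: 1 − 2r²/(1 + ρ)

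If nothing drifts, r = ρ and the ratio is (1 + 2r)/(1 + r)². If a subject's underlying level correlates d between baseline and follow-up, r = ρd. Example with ρ = 0.8 and d = 0.9: r = 0.72 and r² = 0.5184; one covariate leaves 0.4816; two leave 1 − 1.0368/1.8 = 0.4240; the ratio is 0.880, a 12% cut.

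| ρ | d = 1 | d = 0.9 | d = 0.8 |
|---|---|---|---|
| 0.5 | 11% | 8% | 6% |
| 0.7 | 17% | 12% | 8% |
| 0.8 | 20% | 12% | 8% |

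**2. Simulation without drift.** The outcome is percent change. Entry limits apply to the Week -6 value, and response varies between treated subjects. Assumed mean and SD in mg/dL: LDL-C 125 and 30, HDL-C 50 and 11, total cholesterol 205 and 33; triglycerides median 130 with log SD 0.45. Assumed effects: −45%, +5%, −30% and −20% respectively. With a within-subject correlation of 0.5 to 0.8, adding Week -6 cuts the residual variance by:

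- HDL-C: 6.1% to 12.9%
- triglycerides: 5.8% to 11.6%
- total cholesterol: 7.3% to 10.5%
- LDL-C: 2.9% to 6.7% with the 120-190 mg/dL window, 1.4% to 3.8% with 120-160 mg/dL

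The gain for LDL-C is smallest because the entry window narrows the range of the Visit 1 value.

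**3. Simulation with drift, final visit.** The design is the same on the log scale, with assumed within-subject SDs of 6-10% (HDL-C), 18-27% (triglycerides) and 7-12% (LDL-C). A re-run at the middle of these ranges, with between-subject log SDs of 0.20, 0.40 and 0.22, gave these figures to within about a point; the LDL-C figure lies between the results for the two entry windows.

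| Cut in variance of the treatment difference | d = 1 | d = 0.9 | d = 0.8 |
|---|---|---|---|
| HDL-C | about 13% | about 7% | about 4% |
| Triglycerides | about 11% | about 6% | about 4% |
| LDL-C | about 6% | about 3% | about 2% |

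**4. What that is worth.**

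- Standard error: 1 − √(1 − 0.02) = 1.0% at the low end and 1 − √(1 − 0.13) = 6.7% at the high end.
- Equivalent extra subjects on 543: 543 × 0.02/0.98 ≈ 11 and 543 × 0.13/0.87 ≈ 81.
- A comparison with 80% power has power Φ(2.802/s − 1.960) once the standard error is multiplied by s: about 81% at s = 0.99, 82% at 0.97 and 84% at 0.95.

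Non-HDL-C and non-HDL-C/HDL-C were not simulated separately.

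**The case against.** The strongest reply is that this is a preference. ANCOVA on the last pre-dose value is standard, is valid under randomisation, and already goes beyond the protocol's model. That stands: nothing here is an error or a bias.

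The size is also easy to overstate, in three ways:

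- **Equal correlation.** The 11-20% in the first column of the closed form treats samples two years apart as being as alike as samples six weeks apart. With drift the gain roughly halves or worse, so the no-drift figures are close to a best case.
- **TWA figures.** Without drift, the simulated TWA cuts were larger (20-22% HDL-C, 16-18% triglycerides, 4-9% LDL-C). But SAP 3.1.2 and 4.3.4 define the secondary endpoint as change to the final visit, and TWA is an additional analysis. Its figures should not be used as the headline.
- **Error in the denominator.** A reader might infer that error in the baseline passes directly into the residual because baseline is the divisor of the percent change. It does not. The model conditions on baseline, and given baseline the divisor is fixed and only rescales the residual. The loss is regression dilution.

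It can also be said that Week -6 precedes the diet stabilisation that starts at screening (Protocol 3.8), and that entry limits truncate it. Both are reasons not to average it into baseline. Neither rules it out as a covariate, because its coefficient is estimated from the data, and a gain remained in the simulations that applied the limits. The LDL-C reagent change does not interfere: SAP 4.1 describes it as affecting post-baseline values.

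Finally, SAP 4.3.5 switches to rank ANCOVA if the model assumptions fail, which is plausible for triglycerides. A change to the parametric model alone would be incomplete. This point is accepted, and the fix covers it.

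**Conclusion.** This is a free improvement of low priority. The lipid ANCOVA leaves out a pre-randomisation covariate that is already collected. Under the assumptions shown, adding it reduces the variance of the final-visit treatment difference by about 4-13% for HDL-C, 4-11% for triglycerides and 2-6% for LDL-C, which is about 1-7% on the standard error. TWA gains are somewhat larger. The range rests on assumed within-subject variation, between-subject variation and two-year drift; the documents supply none of these.

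A reader might infer that the lipid results are biased, or that a conclusion on HDL-C, triglycerides or the ratio hangs on this. The documents support neither: the planned estimate is unbiased, and they give no effect size or power from which a changed conclusion could be shown. The primary CIMT analysis is a separate model and is unaffected.

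**What to change.** In SAP 4.1, 4.1.5, 4.3.5 and Appendices B and C, add the Visit 1 value of the same lipid as a second covariate, so that the Appendix C model line becomes `MODEL PER_CHG = TRT BASE VISIT1`.

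- **Where it applies:** LDL-C, total cholesterol, HDL-C, triglycerides, non-HDL-C and non-HDL-C/HDL-C, in the final-visit and TWA analyses and in the rank ANCOVA fallback, which accepts more than one covariate. Appendix B currently omits total cholesterol from its lipid row, although 3.1.2 and 4.1 include it; correct that in the same edit.
- **Which value:** Visit 1, or the screening re-test value if one was taken. State this rule in the text.
- **What stays:** the endpoint remains percent change from the existing baseline, and the apolipoprotein models are unchanged.

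The cost is a few lines of SAP text, one model term and one degree of freedom per model, with no new data. Protocol 8.1 allows SAP amendments up to unblinding. The change must be made before then, because a covariate added afterwards would look selective. Record it in SAP section 6 as a departure from the protocol's model.
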